14.4.1 Data and Safety Monitoring Committee

This study will be monitored in accordance with the Children's Oncology Group policy for data and safety monitoring of Phase 1 and 2 studies. In brief, the role of the COG Data and Safety Monitoring Committee is to protect the interests of patients and the scientific integrity for all Phase 1 and 2 studies. The DSMC consists of a chair; a statistician external to COG; one external member; one consumer representative; the lead statistician of the PEP-CTN scientific committee; and a member from the NCI. The DSMC meets at least every 6 months to review current study results, as well as data available to the DSMC from other related studies. Approximately 6 weeks before each meeting of the Phase 1 and 2 DSMC, study chairs will be responsible for working with the study statistician to prepare study reports for review by the DSMC. The DSMC will provide recommendations to the COG PEP-CTN Chair and the Group Chair for each study reviewed to change the study or to continue the study unchanged. Data and Safety Committee reports for institutional review boards can be prepared using the public data monitoring report as posted on the COG Web site.

APPENDIX I: PERFORMANCE STATUS SCALES/SCORES

Karnofsky		Lansky	
Score	Description	Score	Description
100	Normal, no complaints, no evidence of disease	100	Fully active, normal.
90	Able to carry on normal activity, minor signs or symptoms of disease.	90	Minor restrictions in physically strenuous activity.
80	Normal activity with effort; some signs or symptoms of disease.	80	Active, but tires more quickly
70	Cares for self, unable to carry on normal activity or do active work.	70	Both greater restriction of and less time spent in play activity.
60	Required occasional assistance, but is able to care for most of his/her needs.	60	Up and around, but minimal active play; keeps busy with quieter activities.
50	Requires considerable assistance and frequent medical care.	50	Gets dressed, but lies around much of the day; no active play, able to participate in all quiet play and activities.
40	Disabled, requires special care and assistance.	40	Mostly in bed; participates in quiet activities.
30	Severely disabled, hospitalization indicated. Death not imminent.	30	In bed; needs assistance even for quiet play.
20	Very sick, hospitalization indicated. Death not imminent.	20	Often sleeping; play entirely limited to very passive activities.
10	Moribund, fatal processes progressing rapidly.	10	No play; does not get out of bed.

THIS PROTOCOL IS FOR RESEARCH PURPOSES ONLY, SEE PAGE 1 FOR USAGE POLICY

APPENDIX II: CORRELATIVE STUDIES GUIDE**FOR PATIENTS \leq 10 KG:**

Correlative Study	Appx.	Volume per Sample	Total Volume	Tube Type
Pharmacokinetics Study	IV-A	3 ml	24 ml	Vacutainer Tubes
Pharmacodynamics (mRNA Transcript Levels)	V	2 ml	6 ml	Citrate Vacutainer Tubes
Pharmacodynamics (NEDDylated Protein Analysis) – Blood Samples	VI	5 ml	20 ml	Cell Save Tubes and Heparinized Tubes
Pharmacodynamics (NEDDylated Protein Analysis) – Bone Marrow Samples	VII	3 ml	6 ml	Heparinized Tubes
Total Blood + Bone Marrow Volume			56 ml	

THIS PROTOCOL IS FOR RESEARCH PURPOSES ONLY, SEE PAGE 1 FOR USAGE POLICY

FOR PATIENTS > 10 KG:

Correlative Study	Appx.	Volume per Sample	Total Volume	Tube Type
Pharmacokinetics Study	IV-B	3 ml	48 ml	Vacutainer Tubes
Pharmacodynamics (mRNA Transcript Levels)	V	2 ml	6 ml	Citrate Vacutainer Tubes
Pharmacodynamics (NEDDylated Protein Analysis) – Blood Samples	VI	5 ml	20 ml	Cell Save Tubes and Heparinized Tubes
Pharmacodynamics (NEDDylated Protein Analysis) – Bone Marrow Samples	VII	3 ml	6 ml	Heparinized Tubes
Total Blood + Bone Marrow Volume			80 ml	

THIS PROTOCOL IS FOR RESEARCH PURPOSES ONLY, SEE PAGE 1 FOR USAGE POLICY

APPENDIX III: TOXICITY-SPECIFIC GRADING**Bilirubin**

Grade 1:	> ULN - \leq 1.5 x ULN
Grade 2:	> 1.5 x ULN – 3.0 x ULN
Grade 3:	> 3.0 x ULN – 10.0 x ULN
Grade 4:	> 10.0 x ULN

ALT: For the purpose of this study, the ULN for SGPT is 45 U/L regardless of baseline.

Grade 1:	> 45 U/L - \leq 135 U/L
Grade 2:	136 U/L – 225 U/L
Grade 3:	226 U/L – 900 U/L
Grade 4:	> 900 U/L

AST: For the purpose of this study, the ULN for SGOT is 50 U/L regardless of baseline.

Grade 1:	> 50 U/L - \leq 150 U/L
Grade 2:	151 U/L – 250 U/L
Grade 3:	251 U/L – 1000 U/L
Grade 4:	> 1000 U/L

APPENDIX IV-A: PHARMACOKINETIC STUDY FORM FOR PATIENTS \leq 10 KG

COG Pt ID # _____
Please do not write patient names on this form or on samples.

Patient Weight: _____ kg Body Surface Area: _____ m²

MLN4924 (Pevonedistat) Dose Level: _____ mg/m² MLN4924 (Pevonedistat) Total Daily Dose: _____ mg

Blood samples (3 ml) will be collected in chilled Becton-Dickinson Vacutainer K2 EDTA tubes at the following time points during Cycle 1 (\pm 10 min): Day 1 (pre-dose, at the end of MLN4924 [pevonedistat] infusion, and at 4 – 6 hrs, and 24 hrs after the end of MLN4924 [pevonedistat] infusion), and Day 5 (pre-dose, at the end of MLN4924 [pevonedistat] infusion, and at 4 – 6 hrs, and 24 hrs after the end of MLN4924 [pevonedistat] infusion).

Record the exact time the sample is drawn along with the exact time MLN4924 [pevonedistat] infusion begins and ends on Days 1 and 5.

Blood Sample No.	Time Point	Scheduled Collection Time	Actual Date Sample Collected	Actual Time Sample Collected (24-hr clock)
1	Day 1	Prior to MLN4924 infusion	____ / ____ / ____	____ : ____ : ____
		MLN4924 Dose on Day 1 Date: ____ / ____ / ____	Infusion Start Time: ____ : ____	Infusion Stop Time: ____ : ____
2	Day 1	At the end of MLN4924 infusion	____ / ____ / ____	____ : ____ : ____
3	Day 1	4 – 6 hrs after MLN4924 infusion end time	____ / ____ / ____	____ : ____ : ____
4	Day 1	24 hrs after MLN4924 infusion end time	____ / ____ / ____	____ : ____ : ____
5	Day 5	Prior to MLN4924 infusion	____ / ____ / ____	____ : ____ : ____
		MLN4924 Dose on Day 5 Date: ____ / ____ / ____	Infusion Start Time: ____ : ____	Infusion Stop Time: ____ : ____
6	Day 5	At the end of MLN4924 infusion	____ / ____ / ____	____ : ____ : ____
7	Day 5	4 – 6 hrs after MLN4924 infusion end time	____ / ____ / ____	____ : ____ : ____
8	Day 5	24 hrs after MLN4924 infusion end time	____ / ____ / ____	____ : ____ : ____

One copy of this Pharmacokinetic Study Form should be uploaded into RAVE. A second copy should be sent with the samples to the address listed in [Section 8.2.6](#). See [Section 8.2](#) for detailed guidelines for packaging and shipping PK samples.

Signature: _____
(site personnel who collected samples)

Date: _____

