8.2.2 Sampling Schedule (See [Appendix IV-A](#) and [Appendix IV-B](#))

8.2.2.1 For patients ≤ 10 kg, blood samples will be obtained at the following time points during Cycle 1:

THIS PROTOCOL IS FOR RESEARCH PURPOSES ONLY, SEE PAGE 1 FOR USAGE POLICY

- Day 1: pre-dose, at the end of infusion, and at 4 – 6, and 24 hours after the end of infusion
- Day 5: pre-dose, at the end of infusion, and at 4 – 6, and 24 hours after the end of infusion

8.2.2.2 For patients > 10 kg, blood samples will be obtained at the following time points during Cycle 1:

- Day 1: pre-dose, at the end of infusion, and at 1, 2, 4, 6 – 8, and 24 hours after the end of infusion
- Day 3: pre-dose
- Day 5: pre-dose, at the end of infusion, and at 1, 2, 4, 6 – 8, 24, and 48 **OR** 72 hours after the end of infusion

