8.2.3 Sample Collection and Handling Instructions

Blood samples (3 mL) will be collected into a chilled Becton-Dickinson Vacutainer K2 EDTA tube at a site distant from the infusion for pharmacokinetic evaluation. Samples cannot be drawn from the 2nd lumen of a multi-lumen catheter through which drug is being administered. Record the exact time that the sample is drawn along with the exact time that the drug infusion begins and ends.

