8.2.4 Sample Processing

- Collect 3.0 mL of venous blood into a chilled K2EDTA lavender top Becton-Dickinson Vacutainer.
- Gently invert the Vacutainer 8 to 10 times to mix the additive with the collected blood prior to centrifugation and place immediately on ice.
- Centrifuge the Vacutainers for 10 minutes at approximately 1100 to 1300 x g (RCF) at approximately 4°C in a refrigerated centrifuge. Note: if using a collection device other than Becton-Dickinson, refer to manufacturer's instruction for proper centrifugation force and time.
- Immediately following centrifugation, gently remove plasma from the packed cells and transfer into 2 appropriately labeled 2.0 mL cryogenic vials. To ensure a more homogeneous sample, transfer all plasma into one cryovial. From there, split the plasma evenly between the 2 aliquots. A minimum of 0.6 mL needs to be obtained for each aliquot.
- Cap the labeled storage tubes and freeze the plasma samples immediately at approximately -70°C or lower. If a -70°C freezer is not available, freeze and store samples at -20°C. No more than 45 minutes will elapse between blood collection and freezing the plasma sample.
- Store samples frozen at approximately -70°C or lower until shipment.

Note: If a -70°C freezer is not available, the samples may be stored at approximately -20°C in a commercial grade freezer with no auto-defrost until shipment.

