8.4.2 Sampling Schedule (See [Appendix VI-B](#) and [Appendix VII](#))

For questions about the sample delivery process, please contact [name] ([contact]) or [name] ([contact]). Blood samples will only be collected from consenting patients with an initial absolute blast count ≥ 1000 blasts/ μ L (see [Appendix VI-A](#) for details). Blood samples will be collected from consenting patients at the following time points during Cycle 1:

- Day 1: prior to IV azacitidine and MLN4924 (pevonedistat) dose, 10 hours after the end of MLN4924 (pevonedistat) infusion, and 24 hours after the end of MLN4924 (pevonedistat) infusion
 - **NOTE:** The Day 1, Hour 0 sample can be obtained after the IT cytarabine dose.
- At the end of Cycle 1 on the same day as bone marrow evaluation.

Bone marrow aspirate will be collected from consenting patients at the following time points, regardless of initial absolute blast count:

- Pre-study on the same day as bone marrow evaluation
- At the end of Cycle 1 on the same day as bone marrow evaluation

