8.4.3 Sample Collection and Handling Instructions

Blood samples will be collected in Cell Save tubes (3 ml) and heparinized tubes (2 ml). Samples may be collected from a central line. Either lithium heparin or sodium heparin is acceptable. Do NOT use lithium PST (plasma separator tubes). Record the exact time that the sample is drawn along with the exact time that the drug infusion begins. For end of Cycle 1 samples, drug infusion timing is not needed. See [Appendix VI-A](#) for detailed instructions.

Bone marrow samples (3 ml) will be collected in heparinized tubes or in COG shipping media. Record the exact time that the sample is drawn and whether the sample is a pre-study or end of Cycle 1 sample.

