- **If possible, please FAX the bone marrow immunophenotype report with the first peripheral blood sample.** If this is not possible, please send the report that day via [contact]) or email to [name] at [contact] and [name] at [contact] (Please strip HPI identifiers)
- **Ship the sample by Federal Express Priority Overnight delivery to:**

[name] c/o [name]
[name]
[name]
Baylor College of Medicine
[name]
[contact]

Courier information:

- Notify [name] or [name] lab representative prior to shipment of the sample. [contact]. Please email the Fed-Ex tracking number to the email addresses above.
- If possible, do not ship samples for delivery on a weekend or holiday. Weekend samples can be mailed Monday for Tuesday delivery.

**APPENDIX VI-B: PHARMACODYNAMICS (NEDDYLATED PROTEIN ANALYSIS) STUDY
FORM – BLOOD SAMPLES**

COG Pt ID # _____ Cycle 1, Day 1 Date: _____
Please do not write patient names on this form or on samples.

Patient Weight: _____ kg Body Surface Area: _____ m²

MLN4924 (Pevonedistat) Dose Level: _____ mg/m² MLN4924 (Pevonedistat) Total Daily Dose: _____ mg

WBC: _____ /µL % Blasts: _____ %

In consenting patients, blood samples (5 ml) will be collected in Cell Save tubes (3 ml) and heparinized tubes (2 ml) at the following time points during Cycle 1 (\pm 10 min): Day 1 (prior to IV azacitidine and MLN4924 [pevonedistat] dose, 10 hrs after the end of MLN4924 [pevonedistat] infusion, and 24 hrs after the end of MLN4924 [pevonedistat] infusion), and at the end of Cycle 1 on the same day as bone marrow evaluation.

Record the exact time the sample is drawn along with the exact time MLN4924 (pevonedistat) infusion begins and ends on Day 1.

Blood Sample No.	Time Point	Scheduled Collection Time	Actual Date Sample Collected	Actual Time Sample Collected (24-hr clock)
1	Day 1	Prior to MLN4924 dose	____/____/____	____:____
MLN4924 Dose on Day 1		Date: ____/____/____	Infusion Start Time: ____:____	
			Infusion Stop Time: ____:____	
2	Day 1	10 hrs after MLN4924 infusion end time	____/____/____	____:____
3	Day 1	24 hrs after MLN4924 infusion end time	____/____/____	____:____
4	End of Cycle 1	Same day as bone marrow evaluation	____/____/____	____:____

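### For patients of 10 kg or less the plan halves the PK draws but keeps full-size volumes per draw and sets no per-kg limit on research blood, which matters mainly below about 5 kg

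*Combined protocol and SAP*

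**What the plan says.** Section 4.1.1 admits patients from 1 month of age, and no eligibility criterion sets a minimum weight.

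- **PK (required).** Section 8.2.3 fixes one volume for everyone: "Blood samples (3 mL) will be collected into a chilled Becton-Dickinson Vacutainer K2 EDTA tube". The form for patients of 10 kg or less (Appendix IV-A) repeats it: "Blood samples (3 ml) will be collected in chilled Becton-Dickinson Vacutainer K2 EDTA tubes at the following time points during Cycle 1". What changes with weight is the schedule. At 10 kg or less, Section 8.2.2.1 asks for "Day 1: pre-dose, at the end of infusion, and at 4 – 6, and 24 hours after the end of infusion", and the same again from Day 5, so 8 draws in all. Patients above 10 kg have 16.
- **mRNA (optional).** Sections 8.3.2 and 8.3.3 ask for three draws of 2 mL, one of them before the Day 1 dose.
- **NEDDylation blood (optional).** The Appendix VI-B form says "blood samples (5 ml) will be collected in Cell Save tubes (3 ml) and heparinized tubes (2 ml) at the following time points". Section 8.4.2 asks for one sample before azacitidine and pevonedistat on Day 1, then "10 hours after the end of MLN4924 (pevonedistat) infusion, and 24 hours after the end of MLN4924 (pevonedistat) infusion", then one at the end of Cycle 1. Collection also needs an initial absolute blast count of at least 1000/µL (Section 8.4.2) and is omitted when MRD is below 1% (Appendix VI-A).

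Appendix II has a separate table for each weight group. Both list the same volume per sample. Its "Total Blood + Bone Marrow Volume" row reads 56 mL at 10 kg or less and 80 mL above. The supplied text contains no per-kg limit, no limit as a share of blood volume, and no explicit rule on which draw to omit in a small child.

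**The concern.** The plan provides for infants elsewhere: they have their own pevonedistat dose levels (Section 5.4.1) and a dilution rule for restricted fluid volume (Section 9.1.5). For research blood, the only adaptation to size is fewer PK time points. The optional studies keep both their count and their volume. On Day 1 the three schedules overlap, so the draws add up within little more than a day, on top of the safety blood tests in Section 8.1. Patients may enter with hemoglobin just above 8.0 g/dL, with transfusion allowed (Section 4.1.5.6). At stake is an avoidable blood loss in the smallest patients, most of it for exploratory aims 1.3.1 and 1.3.2.

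**Working it through.** **Reproducing Appendix II (draws × volume), 10 kg or less**

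- PK 8 × 3 = 24 mL
- mRNA 3 × 2 = 6 mL
- NEDDylation blood 4 × 5 = 20 mL
- NEDDylation marrow 2 × 3 = 6 mL
- Total 24 + 6 + 20 + 6 = 56 mL, as stated. Blood alone is 50 mL.

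Above 10 kg: 16 × 3 = 48 (48 h or 72 h counted once), and 48 + 6 + 20 + 6 = 80 mL, also as stated.

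**Length of the Day 1 window**

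Azacitidine 15 min (Section 5.2), gap 30-60 min, pevonedistat 60 min, then 24 h: 25.75 to 26.25 h. The 10-40 min azacitidine range in Section 9.2.4 gives 25.7 to 26.7 h.

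**Maximum research blood in that window, 10 kg or less**

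- Required PK: 4 × 3 = 12 mL
- Optional mRNA: 1 × 2 = 2 mL
- Optional NEDDylation: 3 × 5 = 15 mL
- Total 29 mL, of which 17 mL is optional

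A patient above 10 kg gives at most 7 × 3 + 2 + 15 = 38 mL in the same window.

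**Size per kg and as a share of blood volume**

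Share = mL / (weight × blood volume per kg). The weights and the 75-90 mL/kg are assumptions; the documents give neither.

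| Volume | 10 kg | 5 kg | 4 kg |
|---|---|---|---|
| 12 mL (required PK, about 26 h) | 1.2 mL/kg; 1.3-1.6% | 2.4 mL/kg; 2.7-3.2% | 3.0 mL/kg; 3.3-4.0% |
| 29 mL (all studies, about 26 h) | 2.9 mL/kg; 3.2-3.9% | 5.8 mL/kg; 6.4-7.7% | 7.3 mL/kg; 8.1-9.7% |
| 50 mL (all studies, Cycle 1) | 5.0 mL/kg; 5.6-6.7% | 10.0 mL/kg; 11.1-13.3% | 12.5 mL/kg; 13.9-16.7% |

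**Blood needed per PK sample**

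Section 8.2.4 splits the plasma into two aliquots: "A minimum of 0.6 mL needs to be obtained for each aliquot". That is 2 × 0.6 = 1.2 mL plasma. Blood needed = 1.2 / (1 − hematocrit). At an assumed hematocrit of 24% this is 1.2 / 0.76 = 1.6 mL; at 40% it is 1.2 / 0.60 = 2.0 mL. Full plasma recovery is assumed.

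**With 2 mL PK draws and no NEDDylation blood**

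- About 26 h: 4 × 2 + 2 = 10 mL, down from 29
- Cycle 1: 8 × 2 + 3 × 2 = 22 mL, down from 50

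**The case against.** The sponsor can say that 29 mL is a ceiling few patients will reach. This stands. Of the 29 mL, 17 mL needs consent to optional studies, and 15 mL of that also depends on the blast count and MRD. Section 4.1.2.1 admits relapses with as little as 0.1% blasts by flow cytometry, so some patients cannot qualify for the NEDDylation draws. The sponsor did adapt the schedule by halving the PK draws. Entry generally requires relapse or failed induction, so patients near 1 month of age or 4 kg will be rare. Blood products are allowed as needed (Section 7.3). The documents contain no benchmark for an acceptable volume, and a limit in the consent form or local policy cannot be ruled out.

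A reader might also infer that sites working under a local limit would lose required PK, and with it data for primary aim 1.1.3. The documents do not support that. Section 8.2 is headed as required and Sections 8.3 and 8.4 as optional, and Section 2.5 says PK is taken in all patients. This ranks the studies, though it does not say what to do when the volume runs short. Nothing suggests a site would drop a required sample to keep an optional one.

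What remains is that the volumes as written do not scale with size, and nothing in the supplied text limits them.

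**Conclusion.** The point holds as a modest gap in the sampling plan. At 10 kg or less the volume per draw is the same as in larger patients, and no per-kg limit appears in the supplied text. It would be wrong to infer that every small patient gives 29 mL, or that small patients follow the same PK schedule as larger ones: required PK alone is 12 mL in about 26 hours, from half as many draws over the cycle.

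The concern is modest near 10 kg and strongest below about 5 kg. Whether the larger percentages are acceptable is a clinical and ethical judgement; these documents show the size but set no threshold. The figures rest on the assumed weights and blood volume, and on consent to every study with both NEDDylation conditions met. No treatment rule, DLT rule or sample size is affected. Label: cheap improvement.

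**What to change.** For patients of 10 kg or less, amend Sections 8.2 to 8.4, Appendix II and the sampling forms:

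1. State a per-kg limit on research blood, per 24 hours and per cycle. Required PK comes first. Optional mRNA and NEDDylation blood is collected only if the whole planned schedule stays within the limit. The NEDDylation marrow sample is unaffected. The sponsor should choose the limit and give its basis, or point to where one already exists.
2. Reduce the PK draw to what two 0.6 mL plasma aliquots need, about 1.6-2.0 mL of blood at the assumed hematocrits, once the laboratory confirms that this suffices. This keeps the backup aliquot. At a hematocrit of 40%, 2 mL leaves no margin, hence the need for confirmation.

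A blanket ban on NEDDylation blood at 10 kg or less is not needed, because the limit removes it only where the volume is too large.

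The cost is an amendment and revised forms, and the loss of some optional exploratory PD blood in the smallest patients.

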APPENDIX IV-B: PHARMACOKINETIC STUDY FORM FOR PATIENTS > 10 KG

COG Pt ID # _____
Please do not write patient names on this form or on samples.

Patient Weight: _____ kg Body Surface Area: _____ m²

MLN4924 (Pevonedistat) Dose Level: _____ mg/m² MLN4924 (Pevonedistat) Total Daily Dose: _____ mg

Blood samples (3 ml) will be collected in chilled Becton-Dickinson Vacutainer K2 EDTA tubes at the following time points during Cycle 1 (\pm 10 min): Day 1 (pre-dose, at the end of MLN4924 [pevonedistat] infusion, and at 1 hr, 2 hrs, 4 hrs, 6 – 8 hrs, and 24 hrs after the end of MLN4924 [pevonedistat] infusion), Day 3 (pre-dose), and Day 5 (pre-dose, at the end of MLN4924 [pevonedistat] infusion, and at 1 hr, 2 hrs, 4 hrs, 6 – 8 hrs, and 24 hrs after the end of MLN4924 [pevonedistat] infusion, as well as at 48 **OR** 72 hours after the end of MLN4924 [pevonedistat] infusion).

Record the exact time the sample is drawn along with the exact time MLN4924 (pevonedistat) infusion begins and ends on Days 1, 3, and 5.

Blood Sample No.	Time Point	Scheduled Collection Time	Actual Date Sample Collected	Actual Time Sample Collected (24-hr clock)
1	Day 1	Prior to MLN4924 infusion	____ / ____ / ____	____ : ____ : ____
MLN4924 Dose on Day 1		Date: ____ / ____ / ____	Infusion Start Time: ____ : ____	Infusion Stop Time: ____ : ____
2	Day 1	At the end of MLN4924 infusion	____ / ____ / ____	____ : ____ : ____
3	Day 1	1 hr after MLN4924 infusion end time	____ / ____ / ____	____ : ____ : ____
4	Day 1	2 hrs after MLN4924 infusion end time	____ / ____ / ____	____ : ____ : ____
5	Day 1	4 hrs after MLN4924 infusion end time	____ / ____ / ____	____ : ____ : ____
6	Day 1	6 – 8 hrs after MLN4924 infusion end time	____ / ____ / ____	____ : ____ : ____
7	Day 1	24 hrs after MLN4924 infusion end time	____ / ____ / ____	____ : ____ : ____
8	Day 3	Prior to MLN4924 infusion	____ / ____ / ____	____ : ____ : ____
MLN4924 Dose on Day 3		Date: ____ / ____ / ____	Infusion Start Time: ____ : ____	Infusion Stop Time: ____ : ____
9	Day 5	Prior to MLN4924 infusion	____ / ____ / ____	____ : ____ : ____
MLN4924 Dose on Day 5		Date: ____ / ____ / ____	Infusion Start Time: ____ : ____	Infusion Stop Time: ____ : ____
10	Day 5	At the end of MLN4924 infusion	____ / ____ / ____	____ : ____ : ____
11	Day 5	1 hr after MLN4924 infusion end time	____ / ____ / ____	____ : ____ : ____
12	Day 5	2 hrs after MLN4924 infusion end time	____ / ____ / ____	____ : ____ : ____
13	Day 5	4 hrs after MLN4924 infusion end time	____ / ____ / ____	____ : ____ : ____
14	Day 5	6 – 8 hrs after MLN4924 infusion end time	____ / ____ / ____	____ : ____ : ____
15	Day 5	24 hrs after MLN4924 infusion end time	____ / ____ / ____	____ : ____ : ____
16	Day 5	48 hrs after MLN4924 infusion end time*	____ / ____ / ____	____ : ____ : ____
17	Day 5	72 hrs after MLN4924 infusion end time*	____ / ____ / ____	____ : ____ : ____

*Blood samples are to be drawn 48 hours **OR** 72 hours after the Day 5 MLN4924 (pevonedistat) infusion end time.

Do not collect blood for both timepoints.

One copy of this Pharmacokinetic Study Form should be uploaded into RAVE. A second copy should be sent with the samples to the address listed in [Section 8.2.6](#). See [Section 8.2](#) for detailed guidelines for packaging and shipping PK samples.

Signature: _____
(site personnel who collected samples)

Date: _____

